10.2. Other Response Parameters	
11. DATA REPORTING/REGULATORY CONSIDERATIONS	
11.1.Monitoring Plan	23
11.2.Stopping Rules	23
11.3.Data Management	24
11.4.Confidentiality	
12. STATISTICAL CONSIDERATIONS	24
12.1.Endpoints	24
12.2.Analysis Populations	25
12.3.Sample Size	
12.4.Interim analyses	25
REFERENCES	25

APPENDICES

A. Informed Consent Form

B. Participant Eligibility Checklist

C. RTOG CNS Acute Radiation Morbidity Scoring Criteria

D. RTOG CNS Late Radiation Morbidity Scoring Criteria

E. NCI Common Terminology Criteria for Adverse Events (CTCAE) v4.0

- F. EORTC QLQ BN20
- G. EORTC QLQ C30

PROTOCOL SYNOPSIS

TITLE	A PHASE I/II STUDV OF	
	EDACTIONATED STEDEOTACTIC	
	DADIOSUDCEDV TO TDEAT I ADCE	
	DAIN METASTASES	
STUDY DUASE		
INDICATION	Uit Histologially or pathologically proven solid	
INDICATION	tumor malignancy and 1 to 4 total brain	
	material manifold to the second seco	
	with no provious whole brain irrediction	
DDIMADY OD IECTVES	Determine the maximum tolerated dose	
I KIWAKI ODJECIVES	(MTD) CODC \therefore 2.6 $(1 - 1)$	
	(MID) of SRS given in 3 fractions for brain	
	metastases $4.2 - 14.1$ cm ³ and $14.2 - 33.5$ cm ³ .	
SECONDARY OBJECTIVES	1. Determine the local control rate as	
	assessed on MRI and clinical exam.	
	2. Determine short- and long-term adverse	
	effects.	
	3 Determine the distant intra-cranial control	
	rota	
	A Determine the event 11 eventual note	
	4. Determine the overall survival rate.	
	5. Assess the patient's health related quality	
	of life.	
HYPOTHESES	Fractionated SRS treatment of large brain	
	metastases will improve local control and	
	toxicity profile compared to single fraction	
	SRS.	
STUDY DESIGN	The MTD of SRS given in 3 fractions for	
	brain metastases $4.2 - 14.1 \text{ cm}^3$ and $14.2 - 14.1 \text{ cm}^3$	
	33.5 cm^3 will be determined using the 6+6	
	study design.	
PRIMARY ENDPOINTS AND	Primary Endpoint:	
SECONDARY ENDPOINTS	Determine the maximum tolerated dose	
	(MTD) of SRS given in 3 fractions for brain	
	metastases $4.2 - 14.1 \text{ cm}^3$ and $14.2 - 33.5 \text{ cm}^3$.	
	Secondary Endpoints.	
	To latermine the last of the former	
	• 10 determine the local control rate of	
	fractionated SRS for brain metastases	
	4.2 - 14.1 cm ³ and 14.2 - 33.5 cm ³ .	

	• To determine the distant brain control
	rate.
	• To determine the overall survival rate.
	• To determine the short- and long-term
	adverse effects of fractionated SRS for
	brain metastases $4.2 - 14.1 \text{ cm}^3$ and
	$14.2 - 33.5 \text{ cm}^3$.
	• Patient health related quality of life
	will be assessed.
SAMPLE SIZE BY TREATMENT	If all four dose levels are reached, the
GROUP	maximum number of evaluable subjects in each arm is 30: therefore the maximum
	number of subjects for the entire study is 60.
SUMMARY OF SUBJECT ELIGIBILITY	Inclusion Criteria
CRITERIA	• All patients age 18 years and older with
	pathologically proven solid tumor
	malignancy and 1 to 4 brain metastases,
	one of which is $4.2 - 33.5$ cm ³ .
	• Systemic therapy: Prior cytoxic systemic
	therapy must be completed ≥ 5 days prior
	to radiosurgery. No concurrent cytoxic
	systemic therapy along with SRS. Cytoxic
	systemic therapy to start ≥ 5 days after the
	completion of SKS.
	 Prior surgery or SRS is allowed as long as the target metastatic locian in this study has
	not provide hear treated with SPS
	• Detions much avhibit the ability to
	• Patient must exhibit the ability to
	written informed consent
	• Life expectancy of at least 12 weeks
	• Ene expectancy of at least 12 weeks.
	Exclusion Criteria
	• Patients who have previously been treated
	with whole brain irradiation.
	• Patients whose metastatic lesion in
	question had previously been treated with
	SRS.
	• The patient has greater than 4 total brain
	metastases at the time of initial evaluation.

	• Pediatric patients (age <18), pregnant
	women, and patients who are unable to
	give informed consent will be excluded.
INVESTIGATIONAL PRODUCTS	N/A
DOSAGE AND ADMINISTRATION	
CONTROL GROUP	N/A
PROCEDURES	N/A
STATISTICAL CONSIDERATIONS	6+6 design for dose escalation

SCHEMA

Arm	Metastasis Size (cm ³)	Surgical Candidate?	Treatment
1	4.2 - 14.1	Yes	Surgery \rightarrow SRS
2	14.2 - 33.5	Yes	Surgery \rightarrow SRS

Dose Level	Dose Per Fraction	Total Dose
1	8 Gy	24 Gy
2	9 Gy	27 Gy
3	10 Gy	30 Gy
4	11 Gy	33 Gy

AE	Adverse event
CNS	Central nervous system
CR	Complete response
CRF	Case report/Record form
CTCAE	Common Terminology Criteria for Adverse Events
DLT	Dose Limiting Toxicity
DSMB	Data Safety Monitoring Board
IRB	Institutional Review Board
IV	Intravenous
KPS	Karnofsky Performance Scale
MR	Minor response
OS	Overall survival
Р	Progression (disease)
PD	Protocol Director
PFS	Progression free survival
PR	Partial response
QD	Once daily
RECIST	Response evaluation criteria in solid tumors
SAE	Serious adverse event
SD	Stable disease
SRS	Stereotactic Radiosurgery
WBRT	Whole Brain Radiation

LIST OF ABBREVIATIONS AND DEFINITION OF TERMS

1. OBJECTIVES

1.1. **Primary Objectives**

Determine the maximum tolerated dose (MTD) of SRS given in 3 fractions for resection cavities from brain metastases 4.2 - 14.1 cm³ and 14.2 - 33.5 cm³.

1.2. Secondary Objectives

- 1.2.1. Determine the local control rate as assessed on MRI and clinical exam.
- 1.2.2. Determine short- and long-term adverse effects.
- 1.2.3. Determine the distant intra-cranial control rate.
- 1.2.4. Determine the overall survival rate.
- 1.2.5. Assess the patient's health related quality of life.

2. BACKGROUND

2.1.Brain Metastases

Brain metastases are the most common intracranial tumors and occur in approximately 25% of patients with cancer[1]. In the U.S., approximately 170,000 cancer patients a year are diagnosed with brain metastases[2]. Likely as a result of improvements in systemic treatments, the incidence of intracranial metastases has increased over the past decade[3]. The most common malignancies to spread to the brain are lung, breast, kidney, colon/rectum, and melanoma. Clinically, patients with brain metastases can present with headache, neurologic deficits, cognitive dysfunction, seizures, or stroke. Diagnosis is made with neuro-imaging.

The prognosis of patients with brain metastases is variable and depends on several factors, including performance status, age, control of the primary tumor, and extent of extracranial disease[4]. Historically, patients with brain metastases who receive supportive care only have median survival of 1 to 2 months. However, a subgroup of patients with favorable prognosis who undergo treatment can enjoy an extended life expectancy with median survival of 10 to 16 months[5, 6]. Treatment options for brain metastases include medical management, surgery, and radiation. Surgery and radiation will be discussed further.

2.2.Surgery

Surgery has an important role in management of brain metastases. In patients with a large tumor causing mass effect, surgical resection can provide rapid relief of symptoms. Moreover, surgery followed by conventional whole brain radiation (WBRT) decreases local recurrence and improves median survival compared to WBRT alone[7]. In our study, patients deemed suitable for surgery will undergo upfront surgical resection followed by

radiosurgery to the resection cavity.

2.3. Neurocognitive Effects of Whole Brain Radiotherapy

Radiation therapy can be delivered using 1) conventional fractionated radiation to treat the whole brain (WBRT), 2) stereotactic radiosurgery (SRS) to treat individual metastases, or 3) both.

WBRT is associated with a short-term decline in quality of life and long-term deficits in neurocognitive function[8, 9]. In conventionally fractionated WBRT, radiation to the whole cranium is delivered in 10 to 20 daily treatments. Late toxicity of WBRT, such as memory impairment and dementia, is usually irreversible and is likely due to demyelination, vascular damage, and necrosis. Following WBRT, the actuarial rate of neurocognitive toxicity at 2 years can be up to 49%[10]. Meyers reported that 59% of the patients after WBRT demonstrated a greater than 2 standard deviation decline in their performance at 6 months[11]. Results from a recently presented phase III randomized trial reported WBRT to be linked to a marked decline in learning and memory function at 4 months compared to SRS alone (49% vs. 23%, respectively).

2.4. Stereotactic Radiosurgery

Unlike WBRT, stereotactic radiosurgery has the advantage of sparing normal brain. In SRS, high energy radiation is precisely directed at the target lesion. Due to the steep fall–off of the radiation dose away from the target, relative sparing of the normal brain is possible. To minimize the potential late effects of WBRT, investigators have explored the use of SRS alone, deferring the use of WBRT for salvage treatment if needed. Both retrospective analyses[12-15] and a prospective randomized trial[16] reported no apparent survival benefit to combining WBRT with SRS compared to SRS alone.

We have recently published a retrospective review of patients with brain metastases treated with surgical resection followed by adjuvant SRS to the resection cavity while deferring WBRT for salvage. Actuarial local control rates at 6 and 12 months were 88% and 79%, respectively. This value compares favorably with historic results with observation alone (54%) and postoperative WBI (80-90%)[17]. Given its negative neurocognitive effects in the absence of survival benefit, it is our current practice to omit WBRT in favor of SRS in patients with limited number of brain metastases.

2.5.Large Brain Metastases

Neither WBRT nor SRS has been shown to adequately control large brain metastases. WBRT has been shown to have less than 5% complete response rate with brain metastases larger than 2 cm[18]. Radiation Therapy Oncology Group (RTOG) 90-05 study determined maximum tolerated dose (MTD) and subsequent dose selection guidelines for *single* fraction radiosurgery in patients with recurrent brain metastases who had received prior partial or whole brain irradiation[19]. The MTD for metastases < 2cm, 2-3 cm and

3-4 cm were not reached, 24, and 18 Gy, respectively. Based on these results, the recommended *single* fraction radiosurgery dose for brain metastases of <2 cm, 2-3 cm, and 3-4 cm are 24 Gy, 18 Gy, and 15 Gy, respectively. However, subsequent reports on the usage of these dosing guidelines show a local control of only 49% and 45% for metastases 2-3 cm and 3-4 cm in diameter, respectively[20]. Similarly, a series from Pittsburgh showed only a 49% local control rate for tumors >4 cc (approximately >2 cm diameter)[21]. The importance of controlling brain metastases is demonstrated by the significant decline in neurocognitive function in those patients with disease progression compared to those with controlled disease[11]. Given the negative impact of recurrent intracranial disease on the quality of life and neurocognitive ability of patients, a great need exists for the improvement of local control in patients with large brain metastases.

2.6.Fractionated Radiosurgery

One technique which may improve local control and toxicity profile is fractionation of SRS treatments. Fractionation has been demonstrated to increase tumor kill by allowing inter-fraction re-oxygenation and cell reassortment to minimize radioresistance due to hypoxia and cell cycle[22]. In addition, fractionation reduces the late effects of radiotherapy.

Despite the widespread use of fractionated radiosurgery, no prospective data exist to 1) provide dose guidelines, 2) determine whether fractionation of SRS improves local control, and 3) examine the effects of fractionation on acute and late side effects.

The protocol outline here proposes SRS to be delivered in 3 fractions with initial dose of 24 Gy in 3 fractions (i.e., 8 Gy x 3 fractions) for brain metastases $4.2 - 14.1 \text{ cm}^3 (2 - 3 \text{ cm} \text{ diameter})$ and for metastases $14.2 - 33.5 \text{ cm}^3 (3 - 4 \text{ cm} \text{ diameter})$. This dose is radiobiologically equivalent to 16 Gy in a single fraction. This conservative dose of 24 Gy in 3 fractions is below or similar to the MTD for *single* fraction SRS determined in the RTOG 90-05 in patients who had already received previous brain irradiation.

3. PARTICIPANT SELECTION AND ENROLLMENT PROCEDURES

Refer to the Participant Eligibility Checklist in Appendix B.

3.1 Inclusion Criteria

- 3.1.1. All patients age 18 years and older with pathologically proven solid tumor malignancy and 1 to 4 brain metastases, one of which is 4.2 33.5 cm³.
- 3.1.2. Systemic therapy: Prior cytoxic systemic therapy must be completed \geq 5 days prior to radiosurgery. No concurrent cytoxic systemic therapy along with SRS. Cytoxic systemic therapy to start \geq 5 days after the completion of SRS.
- 3.1.3. Prior surgery or SRS is allowed as long as the target metastatic lesion in this study has not previously been treated with SRS.

- 3.1.4. Patient must exhibit the ability to understand and the willingness to sign a written informed consent.
- 3.1.5. Life expectancy of at least 12 weeks.

3.2 Exclusion Criteria

- 3.2.1. Patients who have previously been treated with whole brain irradiation.
- 3.2.2. Patients whose metastatic lesion in question had previously been treated with SRS.
- 3.2.3. The patient has greater than 4 total brain metastases at the time of initial evaluation.
- 3.2.4. Pediatric patients (age <18), pregnant women, and patients who are unable to give informed consent will be excluded.

3.3 Informed Consent Process

- **3.3.1** Informed consent may be obtained by the PI or a designee who is a member of the research team.
- **3.3.2** The PI is ultimately responsible for determining whether a subject has the capacity to consent, although informed consent may be obtained by either the PI or designee. If the subject is lacking such capacity, whether due to cognitive impairment, the subject's age, or other causes, the PI/designee may obtain consent from a legally authorized representative.
- **3.3.3** As part of the consent process, the subject's or his/her representative's questions must be answered prior to consent being given and throughout the study. The subject or his/her representative should be asked if there are any questions prior to consent being obtained and at all subsequent visits or contacts. These elements of the informed consent process must be documented in the patient's medical record.
- **3.3.4** When giving the consent, the subject or a duly authorized legal representative needs to read each page and sign and date the last page of the form along with the investigator or designee obtaining consent.
- **3.3.5** The signed Informed Consent Form should be filed in the following location.
 - **3.3.5.1** The signed consent will be filed in the patient's research study record.
 - **3.3.5.2** One copy of the signed consent will be sent to Stanford Medical Records where it will be scanned into the patient's electronic medical record.
 - **3.3.5.3** An additional copy of the consent form will be filed in the study Regulatory Binder.

3.4 Randomization Procedures

This is not a randomized trial. There will be no randomization.

4. TREATMENT PLAN

4.1 Investigational Agent or Device Administration 4.1.1. PRETREATMENT EVALUATIONS

Patients will be evaluated by a multi-disciplinary team composed of radiation oncologists and neurosurgeons to assess for their eligibility. Patient's oncologic history, presenting symptoms, physical examination, pathology, and imaging studies will be reviewed. Patients will be evaluated for surgical candidacy and resectability.

4.1.2. SURGICAL TREATMENT

Patients who are good surgical candidates, as determined by neurosurgical evaluation, will undergo a surgical resection prior to radiotherapy. All others will receive primary SRS.

4.1.3. RADIATION THERAPY

4.1.3.1.Dose specifications/escalation

SRS will be delivered in 3 fractions. Provided that the MTD has not been reached, the total dose will be increased in 3 Gy increments:

Dose Level	Dose Per Fraction	Total Dose
1	8 Gy	24 Gy
2	9 Gy	27 Gy
3	10 Gy	30 Gy
4	11 Gy	33 Gy

A minimum of six patients will be enrolled per arm:

Arm	
1	4.2 - 14.1 cm ³ brain metastasis following surgical resection
2	14.2 - 33.5 cm ³ brain metastasis following surgical resection

Similar to RTOG 90-05, the dose limiting toxicity (DLT) is defined as grade 3, 4, or 5 RTOG central nervous system (CNS) acute radiation morbidity scoring criteria (Appendix C) observed within 30 days of radiosurgery. The MTD is defined as one dose level below the highest toxic dose (i.e., the DLT dose).

The occurrence of late toxicities will be continuously monitored. If a late DLT occurs in 3 or more out of 6 (or 4 or more out of 12) patients at a certain dose level after the radiation dose had already been escalated to the next level, the MTD will be backtracked to the level

below the one at which the DLTs occurred.

Number of Patients at a Given	Escalation Decision Rule					
Dose Level with a DLT						
0-1 out of 6	Enter 6 patients at the next higher dose level					
2 out of 6	Enter at least 6 more patients at the current dose level.					
	• If 0-1 of these 6 experience a DLT (i.e., 2-3					
	out of 12), then proceed to next dose level.					
	• If 2 or more of these 6 experience a DLT (4 or more out of 12), then dose escalation will be stopped. Six additional patients will be entered at the next lower dose level if only 6 patients were previously entered.					
3 or more out of 6	Dose escalation will be stopped. Six additional patients will be entered at the next lower dose level if only 6 patients were previously entered.					

Does escalation will proceed as follows, with minimum waiting period of 30 days before proceeding with the next higher dose level:

Should a patient not be evaluable at 30 days (due to death or loss to follow-up or discontinuation of the protocol follow-up per patient preference), then additional patients may be enrolled on each arm such that at least 5 of 6 are evaluable and experience no DLT. For example, should one patient be lost to follow up, but the remaining 5 patients have no DLT, then dose escalation may proceed.

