7.2.2. Adverse Event Reporting

7.2.2.1.PIs or designees should report AEs, whether considered treatment related or not, to the CCTO Safety Coordinator per protocol and regulatory timeframes.

Events should be reported within 10 working days of becoming aware of the event (5 days if the event is life-threatening or resulted in death).

- 7.2.2.2.Unanticipated adverse device effects should be reported to FDA, CCTO and participating investigators within 10 working days of becoming aware of the event (5 days if the event is life threatening or resulted in death).
- 7.2.2.3. RTOG central nervous system (CNS) acute radiation morbidity scoring criteria (Appendix C) will be used to grade acute CNS toxicity.
- 7.2.2.4. The Common Terminology Criteria for Adverse Events (CTCAE) version 4.0 will be used for grading of adverse events (Appendix E).

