10. MEASUREMENT OF EFFECT

10.1 Anti-tumor Effect

Subjects will be seen in follow-up at 1, 3, 6, 9, and 12 months following SRS.At each follow-up, neurologic history and examination will be done. MRI with gadolinium will be obtained at 3, 6, 9, and 12 months.

10.1.1 **Definitions**

Early radiation toxicity is defined as those observed within 30 days of SRS. Late radiation toxicity is defined as those observed after 30 days following SRS. Tumor response will be measured using MRI with gadolinium obtained at 3, 6, 9 and 12 months following SRS.

10.1.2 **Disease Parameters**

Target lesion is defined as those treated with radiosurgery. The size and volume of the target lesion will be measured using the treatment planning software.

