10.2 Other Response Parameters

The primary endpoint of this study is to determine the MTD of tri-fraction SRS. The MTD is defined as one dose level below the highest toxic dose (i.e., the DLT dose). Similar to RTOG 90-05, the dose limiting toxicity (DLT) is defined as grade 3, 4, or 5 RTOG central nervous system (CNS) acute radiation morbidity scoring criteria (Appendix C) observed within 30 days of radiosurgery.

The occurrence of late toxicities will be continuously monitored. If a late DLT occurs in 3 or more out of 6 (or 4 or more out of 12) patients at a certain dose level after the radiation dose had already been escalated to the next level, the MTD will be backtracked to the level

below the one at which the DLTs occurred.

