4.	Does one of the tumors mentioned in (3) have a volume of $4.2 - 33.5$ cm ³ ? (Yes)			
5.	Has the patient completed cytotoxic systemic therapy \geq 5 days prior to radiosurgery? (Yes)			
6.	Will cytotoxic systemic therapy be administered concurrent with SRS? (No)			
7.	Will the patient receive cytotoxic systemic therapy ≤5 days after the completion of SRS? (No)			
8.	Has the target metastatic lesion undergone previous SRS? (No)			

9.	Patient signed informed consent? (Yes)		
10	. Life expectancy of at least 12 weeks? (Yes)		
	Exclusion Criteria (From IRB approved protocol)		
1.	Has the patient previously been treated with whole brain irradiation? (No)		
2.	Has the metastatic lesion in question previously been treated with SRS? (No)		
3.	Does the patient have greater than 4 total brain metastases at the time of initial evaluation? (No)		
4.	Is the patient a pediatric patient (age <18), pregnant woman, or unable to give informed consent? (No)		

*All subject files must include supporting documentation to confirm subject eligibility. The method of confirmation can include, but is not limited to, laboratory test results, radiology test results, subject self-report, and medical record review.

IV. Statement of Eligibility

By signing this form of this trial I verify that this subject is [eligible / ineligible] for participation in the study. This study is approved by the Stanford Cancer Institute Scientific Review Committee, the Stanford IRB, and has finalized financial and contractual agreements as required by Stanford School of Medicine's Research Management Group.

Treating Physician Signature:	Date:
Printed Name:	/
Secondary Reviewer Signature:	Date:
Printed Name:	
Study Coordinator Signature:	Date:
Printed Name:	

a.

C. RTOG CNS ACUTE RADIATION MORBIDITY SCORING CRITERIA

- 0. No Change
- 1. Fully functional status (i.e., able to work) with minor neurologic findings. No medication needed.
- 2. Neurologic findings present sufficient to require home case; nursing assistance may be required; medications including steroids and anti-seizure agents may be required.
- 3. Neurologic findings requiring hospitalization for initial management.
- 4. Serious neurologic impairment which includes paralysis, coma, or seizures > 3 per week despite medication. Hospitalization required.
- 5. Death

D. RTOG CNS LATE RADIATION MORBIDITY SCORING CRITERIA

- 0. None
- 1. Mild headache; slight lethargy
- 2. Moderate headache; great lethargy

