- 3. Severe headaches; severe CNS dysfunction (partial loss of power or dyskinesia)
- 4. Seizures or paralysis; Coma
- 5. Death

E. NCI Common Terminology Criteria for Adverse Events (CTCAE) v4.0

See Nervous System Disorders at: http://evs.nci.nih.gov/ftp1/CTCAE/About.html

- Grade1 Mild; asymptomatic or mild symptoms; clinical or diagnostic observations only; intervention not indicated.
- Grade2 Moderate; minimal, local or noninvasive intervention indicated; limiting ageappropriate instrumental ADL*.
- Grade3 Severe or medically significant but not immediately life-threatening; hospitalization or prolongation of hospitalization indicated; disabling; limiting self care ADL**.

Grade4 Life-threatening consequences; urgent intervention indicated.

Grade5 Death related to AE.

Activities of Daily Living (ADL):

*Instrumental ADL refer to preparing meals, shopping for groceries or clothes, using the telephone, managing money, etc.

**Self care ADL refer to bathing, dressing and undressing, feeding self, using the toilet, taking medications, and not bedridden.

F. EORTC QLQ - BN20

Patients sometimes report that they have the following symptoms. Please indicate the extent to which you have experienced these symptoms or problems during the past week.

During the past week:	Not at all	A Little	Quite a Bit	Very Much
31. Did you feel uncertain about the future?	1	2	3	4
32. Did you feel you had setbacks in your condition?	1	2	3	4
33. Were you concerned about disruption of family life?	1	2	3	4
34. Did you have headaches?	1	2	3	4
35. Did your outlook on the future worsen?	1	2	3	4
36. Did you have double vision?	1	2	3	4
37. Was your vision blurred?	1	2	3	4
38. Did you have difficulty reading because of your vision?	1	2	3	4
39. Did you have seizures?	1	2	3	4
40. Did you have weakness on one side of your body?	1	2	3	4
41. Did you have trouble finding the right words to express yourself?	1	2	3	4
42. Did you have difficulty speaking?	1	2	3	4
43. Did you have trouble communicating your thoughts?	1	2	3	4
44. Did you feel drowsy during the daytime?	1	2	3	4
45. Did you have trouble with your coordination?	1	2	3	4
46. Did hair loss bother you?	1	2	3	4
47. Did itching of your skin bother you?	1	2	3	4
48. Did you have weakness of both legs?	1	2	3	4
49. Did you feel unsteady on your feet?	1	2	3	4

50. Did you have trouble controlling your bladder?	1	2	3	4
© Copyright 1994 EORTC Quality of Life Group. (phase IV module)				

36 of 34

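### The late-toxicity backtracking rule, as worded, does not cover the top dose: no stated rule links late toxicity at 33 Gy to the MTD

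*Combined protocol and SAP*

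**What the plan says.** Section 4.1.3.1 sets four total doses: 24, 27, 30 and 33 Gy. It limits a DLT to RTOG acute CNS grade 3 to 5 events "observed within 30 days of radiosurgery. The MTD is defined as one dose level below the highest toxic dose (i.e., the DLT dose"). Escalation waits at least 30 days.

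The same section adds a rule for late events. If 3 of 6, or 4 of 12, patients have a late DLT "at a certain dose level after the radiation dose had already been escalated to the next level", the MTD moves to the level below. Sections 10.2 and 11.2 repeat the rule with the same condition ("after the radiation dose had already been escalated to the next level").

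Section 10.1.1 defines the late period: "Late radiation toxicity is defined as those observed after 30 days following SRS". Section 7.1.2 lists radiation necrosis, focal deficits and dementia among the late effects. On grading, section 7.2.2 says only that the "acute radiation morbidity scoring criteria (Appendix C) will be used to grade acute CNS toxicity". Appendix D reproduces the "RTOG CNS LATE RADIATION MORBIDITY SCORING CRITERIA", but no section ties that scale to the backtracking rule.

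**The concern.** The backtracking rule is the only stated route from late events to the MTD. Its condition requires that the dose has moved on to a higher level, and after 33 Gy there is none. The general MTD definition does not clearly fill the gap, because it needs a DLT dose and a DLT is confined to the first 30 days.

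The same late toxicity would therefore be handled differently at 30 Gy and at 33 Gy only because the dose table ends. Passing all four levels is a planned outcome: section 12.3.1 states the maximum sample size for that case. At stake is whether the highest dose tested is carried forward as tolerated after meeting the plan's own threshold for late harm.

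**Working it through.** The plan gives no late rates and no operating characteristics for this rule, so there is no plan figure to reproduce. The maximum of 30 per arm in 12.3.1 is not used here.

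**Step 1. Where the rule can act.**

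| Level | Total dose | Next level exists? | MTD after 3 of 6 late DLTs, as worded |
|---|---|---|---|
| 1 | 24 Gy | yes | a level below, which does not exist |
| 2 | 27 Gy | yes | 24 Gy |
| 3 | 30 Gy | yes | 27 Gy |
| 4 | 33 Gy | no | rule does not apply |

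If acute DLTs stop escalation at level 4, level 3 has been escalated from and is covered. The gap is confined to an arm that passes level 4.

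**Step 2. Chance of passing all four levels.** Let X and Y be Bin(6, p), with p the acute DLT rate. P(pass a level) = P(X≤1) + P(X=2) × P(Y≤1). At p = 10%: 0.8857 + 0.0984 × 0.8857 = 0.9729. Two assumed acute patterns:

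- Flat 10%: 0.9729^4 = 0.8959.
- Rising 5/10/20/30%: 0.9968 × 0.9729 × 0.8164 × 0.5564 = 0.4405.

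Given a pass at p = 10%, the share of levels expanded to 12 patients is 0.0984 × 0.8857 / 0.9729 = 0.0896.

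**Step 3. Chance of meeting the plan's threshold at level 4**, for an assumed late rate q (observed and SRS-related):

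| q | 10% | 20% | 30% | 40% | 50% |
|---|---|---|---|---|---|
| P(at least 3 of 6) | 0.016 | 0.099 | 0.256 | 0.456 | 0.656 |
| P(at least 4 of 12) | 0.026 | 0.205 | 0.508 | 0.775 | 0.927 |

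**Step 4. Net chance per arm of an ignored level-4 signal.** Let t_i be the trigger probability at level i, a mix of the 6- and 12-patient values. Net = P(pass all) × (1−t1)(1−t2)(1−t3) × t4, with acute and late events assumed independent. Example, flat 10% acute and late rates 10/20/30/40%:

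- t4 = 0.9104 × 0.4557 + 0.0896 × 0.7747 = 0.4843
- no trigger at levels 1-3 = (1−0.0167)(1−0.1084)(1−0.2783) = 0.6327
- net = 0.8959 × 0.6327 × 0.4843 = 0.27

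**Step 5. Allow for death.** Section 2.1 gives a median survival of 10 to 16 months for favorable patients; exponential survival is assumed. For a 12-month late rate q in patients alive at month 1, h = −ln(1−q)/11, m = ln2/median, and the observed rate is h/(h+m) × (1 − exp(−11(h+m))). Rates of 20/30/40/50% are then observed as about 14/21/29/37% (median 10 months) or 16/24/32/41% (16 months). Applied at every level:

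| Late rates, levels 1-4 | Flat acute: no death | median 10 | median 16 | Rising acute: no death | median 10 | median 16 |
|---|---|---|---|---|---|---|
| 5/10/15/20% | 0.09 | 0.04 | 0.05 | 0.05 | 0.02 | 0.03 |
| 5/10/20/30% | 0.22 | 0.11 | 0.14 | 0.12 | 0.06 | 0.08 |
| 10/20/30/40% | 0.27 | 0.19 | 0.23 | 0.14 | 0.11 | 0.12 |
| 20/30/40/50% | 0.20 | 0.23 | 0.24 | 0.10 | 0.12 | 0.12 |

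The last row rises with death because fewer arms are backtracked at lower levels. With late rates 5/5/10/10%, the net is about 0.015 or less.

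**Step 6. Why a late DLT needs attribution.** Appendix D grade 4 reads "Seizures or paralysis; Coma" and grade 5 is death. Among patients alive at month 1, deaths by month 12 are 1 − exp(−11 ln2/median) = 0.53 (median 10) or 0.38 (median 16). Counting every death would meet 3 of 6 with probability 0.72 or 0.41 without any radiation harm.

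**The case against.** The best counter-argument is that the condition only explains why the revision is called backtracking: late events surface after the 30-day wait. If a late DLT counts as a DLT at 30 Gy, three at 33 Gy could make 33 Gy the toxic dose, and the MTD would be 30 Gy. This lenient reading is available. It conflicts with the 30-day DLT definition and sets aside a condition stated three times, so the primary endpoint would rest on an unwritten choice.

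The argument does limit the claim. A reader might infer that no amount of late toxicity at 33 Gy could ever change the MTD. The documents do not support that: the strict 30-day reading it needs would also leave late DLT without meaning at levels 1 to 3. A reader might also infer that such an arm would be declared as MTD not reached. The plan never says what is declared when all four levels pass; section 2.5 only reports that outcome for one size group of the earlier single-fraction trial ("3-4 cm were not reached, 24, and 18 Gy, respectively").

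Other points stand. No participant is escalated beyond 33 Gy. Late toxicity is continuously monitored, assessed at 3 to 12 months and every 3 to 6 months afterwards (4.4), seen by the DSMC (11.1) and reported as a secondary endpoint (12.1.2). None of these provisions carries an MTD rule. All the late rates above are assumptions, and section 4.5 may further reduce observed late events by removing patients at progression.

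**Conclusion.** The concern holds in limited form. As worded, backtracking does not cover level 4, and no other stated rule links late toxicity at 33 Gy to the MTD. An arm passing all four levels acutely could leave 33 Gy treated as tolerated with 3 of 6 or 4 of 12 late DLTs, while the same count at 30 Gy would lower the MTD to 27 Gy.

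The size depends on assumed rates. With late rates reaching 20-50% at level 4, an ignored signal with no earlier backtracking occurs in about 0.05-0.27 of arms without death and 0.02-0.24 with death. At a 10% level-4 rate the problem is negligible. These figures also assume independent acute and late events and exponential survival.

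Severity: should be fixed. The gap affects the primary-endpoint classification, not dose exposure within the trial.

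**What to change.** In 4.1.3.1, 10.2 and 11.2:

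1. Delete "after the radiation dose had already been escalated to the next level", so that 3 of 6 or 4 of 12 applies at every level including level 4, with the MTD one level below. If level 1 triggers, state that no tested dose is tolerated.
2. State that this rule overrides the general MTD definition.
3. Define a late DLT as Appendix D grade 3 to 5, first observed after day 30 and at least possibly related to SRS on the 7.2.1.1 attribution scale. Set no upper time limit: the present rule has none, and toxicity evaluation continues after month 12, so a 12-month cutoff would weaken protection at levels 1 to 3.
4. Allow the MTD to be reported once the last level's patients have completed the 12-month visit, died or been lost, still subject to backtracking for later events.

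The change is wording only. It adds no visits, scans or patients, and the 30-day escalation wait is unchanged. The costs are attribution judgments on late CNS events, a later final MTD, and a possibly lower one: probability 0.02 (3 of 6) to 0.03 (4 of 12) if the level-4 late rate is 10%, and 0.10 to 0.21 if it is 20%.
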